### **Data analyses**

To summarize participant characteristics, descriptive data included means and standard deviations for continuous variables and counts for categorical variables. Percentages were reported to specify whether recruitment and retention goals were met based on power analysis. For Phase I, a 2 (group) X 4 (time) repeated measures mixed model ANOVA was

\* BodiTrak. Model BT1526-8578. Vista Medical Ltd [name]

† iPad. Apple Inc. [name]

‡ Body Align Pro. serial number 86300861. Motion Unlimited Corporation California. [name].

used to examine the whether the demonstration, instructions, and set up differentiated between focus of attention groups at the different timepoints of the study. Phase II utilized both a 2 (group) X 3 (time) and 2 (group) X 4 (time) mixed model ANOVA to analyze the relationship of focus of attention on performance during the different timepoints. Data including long term retention trials were examined separately due to high attrition rates. If the sphericity assumption was violated, Huynh-Feldt (H-F) and Greenhouse Geisser (G-G) corrections were used to correct the degrees of freedom to report F values. When the overall model was significant, the post hoc pairwise comparison was used, with a Bonferroni correction, to examine differences between every two timepoints in each group. Adverse events would be counted as any falls or health issues requiring medical attention such as a cardiac event.

\* BodiTrak. Model BT1526-8578. Vista Medical Ltd [name]

† iPad. Apple Inc. [name]

‡ Body Align Pro. serial number 86300861. Motion Unlimited Corporation California. [name].

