## **Protocol**

### **Study design**

This was a two phase feasibility study exploring appropriate management, setting, participants including inclusion and exclusion criteria, attrition rates, protocol, and retention. Outcome data for each stage were collected during baseline, acquisition, short-term, and long-term retention. The study was approved by the Institutional Review Board at both Western Carolina University, reference number 949671-4, and Mission Health Systems, reference number 1124795-3. Minimal exertion during the activity was the only potential harm for this study. All participants provided written informed consent prior to data collection. There were no outside funding sources.

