## **Recruitment and retention**

Twelve adults with chronic stroke (mean age  $61.4 \pm 13.8$  years; 6 months to 13 years post-unilateral stroke) with good trunk control (Function in Sitting Test mean score  $51 \pm 2.9/56$ ) were recruited for Phase I. Recruitment of participants was primarily from

\* BodiTrak. Model BT1526-8578. Vista Medical Ltd [name]

† iPad. Apple Inc. [name]

‡ Body Align Pro. serial number 86300861. Motion Unlimited Corporation California. [name].

outpatient settings, local physical therapy clinics or physician offices, located in a rural area, thus the sample size was limited.

To allow for recruitment of a larger sample than in Phase I, Phase II was conducted in an inpatient setting. Participants were recruited via staff physical and occupational therapists at the facility. Twenty-six adults post-acute stroke (mean age  $61.8 \pm 17$ , 1-10 weeks post unilateral stroke), with good trunk control (Function in Sitting Test mean score  $51.3 \pm 4.4$  out of 56) were recruited.

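### A percentage of a power-based goal, given only the totals 12 and 26, cannot show whether either setting could supply a randomised study; the retention denominator is unstated

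*Combined protocol and SAP*

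**What the plan says.** The Study design section sets the aims: "This was a two phase feasibility study exploring appropriate management, setting, participants including inclusion and exclusion criteria, attrition rates, protocol, and retention". Setting, attrition and retention are therefore questions the study means to answer, and the Investigators section shows that a randomised controlled study is the intended next step.

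The only stated yardstick is in Data analyses: "Percentages were reported to specify whether recruitment and retention goals were met based on power analysis". No numeric goal, power-analysis input or denominator appears anywhere.

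Recruitment and retention gives one total per phase: 12 people with chronic stroke and 26 with acute stroke. For Phase I it adds that recruits came mainly from "outpatient settings, local physical therapy clinics or physician offices, located in a rural area, thus the sample size was limited". For Phase II it explains: "To allow for recruitment of a larger sample than in Phase I, Phase II was conducted in an inpatient setting". It then says: "Participants were recruited via staff physical and occupational therapists at the facility". No recruitment period is given for either phase, and no number screened, eligible or approached.

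Three other sections bear on the point. Setting places Phase I in two outpatient clinics. Study Participants says that exclusions were changed while Phase II was under way. Procedures fixes the retention tests at 5 minutes and at 7 to 10 days. Data analyses calls attrition high but gives no count.

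**The concern.** A goal taken from a power analysis answers how many people are needed to detect an assumed difference. It does not say how many people a clinic or ward can provide. The percentage reached moves with two things unrelated to supply: the effect size that was assumed, and how long recruitment stayed open. The number of sites is also hidden in the total.

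The planners of the randomised study need to know how long recruitment would take and in how many sites. With totals alone, 26 looks better than 12, but the two were obtained over unknown periods and apparently from different numbers of sites. A setting could be chosen, and a trial duration planned, on figures that support neither.

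Retention raises a separate, smaller question. If the retained number is divided by the power-based target, a shortfall in recruitment appears as poor retention. If it is divided by those allocated, it does not. The text does not say which was done.

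**Working it through.** There is no stated goal or sample size to reproduce, so the check asks what the yardstick can and cannot reveal.

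**Inputs from the document.** Recruited: 12 (Phase I) and 26 (Phase II), from Recruitment and retention. Sites: two clinics in Phase I, from Setting; one in Phase II, inferred from the singular "facility" in Recruitment and retention. Time open: not given.

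**1. Dependence on the assumed effect size.** Assume a two-sided 5% test, 80% power, 1:1 allocation, two means, the normal approximation and no dropout allowance. None of these is in the document. With standardised effect d, n per arm = 2(1.96 + 0.84)²/d², rounded up.

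| d | n per arm | Total goal | 12 as % of goal | 26 as % of goal |
|---|---|---|---|---|
| 0.5 | 63 | 126 | 10% | 21% |
| 0.8 | 25 | 50 | 24% | 52% |
| 1.0 | 16 | 32 | 38% | 81% |
| 1.2 | 11 | 22 | 55% | 118% |

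The Phase II result moves from clear failure to success with nothing changed in recruitment.

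**2. Blindness to time.** The percentage is the same whatever the period. With assumed periods for the 26 recruits and exact Poisson 95% CIs:
- 3 months: 26/3 = 8.7 per month (5.7 to 12.7)
- 12 months: 26/12 = 2.2 per month (1.4 to 3.2)
- 24 months: 26/24 = 1.1 per month (0.7 to 1.6)

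For the 12 recruits in Phase I the rates are 4.0, 1.0 and 0.5 per month.

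**3. Break-even between settings.** Let T1 and T2 be the months open in Phases I and II.
- Ignoring sites, Phase II was faster if 26/T2 > 12/T1, that is, if T2/T1 < 26/12 = 2.17.
- Per site, with two clinics against one facility, Phase II was faster if 26/T2 > (12/2)/T1, that is, if T2/T1 < 26/6 = 4.33.

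**4. Uncertainty even with equal time open.** Given 38 recruits in all, the exact 95% interval for the Phase II share (26/38) is 0.5135 to 0.8250. Converting by p/(1 − p) gives a rate ratio of 1.06 to 4.71 around 2.17. Doubling the unrounded limits for two sites against one gives 2.11 to 9.43 around 4.33. Both intervals assume equal time open and Poisson counts.

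**5. Retention illustration.** Every number here is assumed except that 26 were recruited: target 34, all 26 allocated, 15 tested at long-term retention.
- Against the target: 15/34 = 44%.
- Against those allocated: 15/26 = 58%.
- The gap is the recruitment shortfall: 26/34 = 76%, and 0.76 × 0.58 = 0.44.

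**The case against.** Five points can be made on the other side.

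- **A reader might infer that retention, like recruitment, lacks a time base and an eligible denominator.** The document does not support that. Its timepoints are stated (5 minutes, 7 to 10 days), and its natural denominator is those allocated, not those eligible.
- **A reader might infer that retention was in fact divided by the power-based target.** Data analyses does not say so. Completers over those enrolled, set against a goal that came from a power analysis, fits the sentence as well. The 44% against 58% therefore shows what one reading would do, not what was done. This stands, and it limits the retention point to an unstated denominator. For recruitment, percentage of the goal is the natural reading but is not spelled out either.
- **The settings are not compared formally, and the move had another reason.** Setting explains that Phase I showed no group differences and that larger ones were expected in acute stroke. This stands in part: the phases differ in population as well as setting, so no rate comparison isolates setting. But setting is a named aim, and sample supply is the reason given in Recruitment and retention.
- **The Poisson interval may not apply.** If a phase closed on reaching a fixed number, the count is not a Poisson outcome. This stands as a caveat on step 4. The break-even ratios do not depend on it.
- **A count of eligible people may be unrecoverable.** Both phases are reported as finished, no referral log is mentioned, Phase I drew on several sources, and Phase II exclusions changed during the study. This stands, so uptake cannot carry the fix.

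**Conclusion.** The point holds for recruitment. A percentage of a power-based goal, with only the totals 12 and 26 beside it, cannot show whether either setting could supply a randomised study. The Phase II percentage ranges from 21% to 118% across assumed effects of 0.5 to 1.2, and no time open is given. Per site, inpatient recruitment was faster only if Phase II was open for less than 4.33 times as long as Phase I. That figure rests on reading Phase II as a single facility; ignoring sites, it is 2.17. The document does not show that inpatient recruitment was slower or faster, and neither should be inferred.

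For retention the conclusion is conditional: the denominator must be stated, and if it is the power-based target, the percentage mixes two different failures.

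The ANOVA is unaffected. What is left unanswered is a stated feasibility aim, so the change should be made.

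**What to change.** In Data analyses, replace the percentage of a power-based goal with two figures for each phase:

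1. Participants consented per site per month open, with an exact 95% CI, and with the opening and closing dates and number of sites stated. If a phase closed at a fixed number, say so.
2. Participants tested over participants allocated, at each timepoint and by arm, with a 95% CI.

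Base any statement about setting on these figures, and note beside it that the phases also differ in population (chronic against acute stroke).

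Report consented over eligible only where screening records exist, under the exclusion criteria in force at the time. Where they do not exist, state that uptake is unavailable and keep a referral tally in the next study.

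Cost: items 1 and 2 should need only consent and session records. Written consent was obtained, but that its dates were kept is an assumption. No extra participants or procedures are needed. The one downside is a little record keeping for the future tally.

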### **Randomization and blinding**

During Phase I, stratified randomization was used based on gender. Results from a 2013 study showed significant differences between gender during focus of attention trials suggesting the potential need for randomization based on gender. Group allocation was randomly selected for the first male and first female participants. Each following participant was alternately placed in either the internal or external focus of attention group. During Phase II, gender-based stratification was not used, to explore whether the intervention groups would naturally be comparable based on gender, age, BMI, and Function in Sitting Test scores. Instead, a blocked randomization with a random number generator (blocks of 10) was used to determine the order of focus group allocation. A blinded statistician and a graduate assistant performed the random number generation and placed the group assignments into separate envelopes, which were then sealed. Group assignment remained in sealed envelopes until after baseline measurements were completed. The participants and statistician were blinded for both phases of the feasibility study.

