### **Procedures**

\* BodiTrak. Model BT1526-8578. Vista Medical Ltd [name]

† iPad. Apple Inc. [name]

‡ Body Align Pro. serial number 86300861. Motion Unlimited Corporation California. [name].

During Phase I, individuals in both groups sat unsupported on a hi-lo mat table which was adjusted so participants were sitting at 90 degrees hip and knee flexion with feet shoulder width apart. Tape marks were used to mark initial set up ensuring standardized positioning for each trial. Following baseline trials, all participants watched the same instructional video describing lateral weight shifting. The instructions included correct mechanics that should be used when weight shifting laterally with focus on correct form needed for the movement.

Testing included baseline, acquisition, short term retention (5 minutes later), and long-term retention (7-10 days later). Participants performed three trials of seated weight shifting to each side at all timepoints. During acquisition, the internal focus group was instructed to “shift your weight as much as possible towards your right or left hip without using your arms”. The external focus group sat with targets one arm length away at shoulder height and were instructed to “shift your body weight as much as possible towards the blue/orange target without using your arms.” During baseline and retention trials, adults were instructed to “lean as far as you can to the right/left without using your arms.” During Phase II, the protocol was similar except 6 trials were performed for acquisition to potentially improve motor learning, which was not significant in Phase I per retention data. Other changes to the protocol included allowing participants to move their feet when weight-shifting. Instructions were also revised. The external focus group was told to “move your shoulder as close to the blue/orange target as possible”, while the internal focus group was told to “shift your body weight as much as possible towards your right/left hip without using your arms.” These instructions were too dissimilar and had

\* BodiTrak. Model BT1526-8578. Vista Medical Ltd [name]

† iPad. Apple Inc. [name]

‡ Body Align Pro. serial number 86300861. Motion Unlimited Corporation California. [name].

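### The ANOVAs count pre-intervention baseline as an outcome level, do not adjust for it, and never name the term that tests focus of attention

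*Combined protocol and SAP*

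**What the plan says.** Study design lists the collection points: "Outcome data for each stage were collected during baseline, acquisition, short-term, and long-term retention".

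Data analyses gives the models. For the first phase: "For Phase I, a 2 (group) X 4 (time) repeated measures mixed model ANOVA was". For the second: "Phase II utilized both a 2 (group) X 3 (time) and 2 (group) X 4 (time) mixed model ANOVA". It adds: "Data including long term retention trials were examined separately due to high attrition rates". No covariate appears in any model.

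The purpose of the models is worded in general terms. Phase I asks whether the set-up and instructions "differentiated between focus of attention groups at the different timepoints of the study". Phase II aims "to analyze the relationship of focus of attention on performance during the different timepoints". Neither statement says whether the group main effect or the group x time interaction is the test. The Bonferroni-corrected follow-up, used only after a significant overall model, compares pairs of timepoints inside each group.

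Randomization and blinding, in the text on Phase II, says: "Group assignment remained in sealed envelopes until after baseline measurements were completed". Procedures begins its account of the neutral wording with "During baseline and retention trials, adults were instructed to" and gives one instruction for everyone. The two groups' instructions differ only at acquisition.

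**The concern.** Baseline is measured before the groups are treated differently, so the focus instruction cannot have acted on it. Baseline is useful as information about how far each person could already shift, but it is not an outcome of the intervention. Treating it as one more outcome level has consequences that depend on which term is read, and the plan leaves that open.

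- **Group main effect:** the estimate averages a level where no effect can exist with the levels where one can.
- **Group x time:** baseline serves as the reference, so there is no such averaging. The test is still spread over 2 or 3 df, and it uses baseline as an unadjusted change rather than as a covariate.
- **Follow-up:** comparing timepoints inside each group does not give a between-group contrast at acquisition or at retention.

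The plan therefore has no named, directly estimated group difference after baseline. That difference, with its confidence interval, is what the later randomized study mentioned under Investigators needs for its design. It also bears on how Phase I is read, because the Setting section uses that phase's non-significant group comparison as part of the reason for changing population.

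**Working it through.** **Time levels.** Four levels out of four collection points must include baseline. Long-term retention was handled separately because of attrition, so the 2 x 3 levels are taken to be baseline, acquisition and short-term retention. This is an inference, because the levels are not listed.

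**Dilution of the group main effect.** For a constant post-baseline difference d the estimate is (0 + d + d)/3 = 2d/3 in the 2 x 3, and (0 + d + d + d)/4 = 3d/4 in the 2 x 4. This needs no assumption about correlation.

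**Inputs for power.** The documents give 26 participants (Phase II) and 12 (Phase I). They mention a power analysis but state no alpha, effect size, SD, correlation or attrition rate, so there is no figure to reproduce. Assumed: equal arms (n = 13 or 6), two-sided alpha 0.05, SD 1, d = 0.8, and the same correlation r between any two timepoints.

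**Formulas** (T levels including baseline, N = 2n, noncentrality NC):
- Main effect: NC = [d(T-1)/T]^2 / {(2/n)[1+(T-1)r]/T}, on 1 and N-2 df.
- Group x time: NC = (n/2) d^2 [(T-1)/T]/(1-r), on T-1 and (T-1)(N-2) df.
- Baseline-adjusted post-baseline mean: NC = d^2 / {(2/n)[(1+(T-2)r)/(T-1) - r^2]}, on 1 and N-3 df.
- Baseline-adjusted difference at acquisition alone: NC = d^2 / {(2/n)(1-r^2)}, on 1 and N-3 df.

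The adjusted rows in the table are also averaged over chance baseline imbalance between arms, which costs up to about 0.02 in power at n = 13.

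**2 x 3, n = 13, numbers in** (r = 0.5 / 0.7):
- Main effect: 0.533^2/0.1026 = 2.77; 0.533^2/0.1231 = 2.31.
- Group x time: 6.5 x 0.64 x (2/3) = 2.773; divided by 0.5 gives 5.55, and by 0.3 gives 9.24.
- Adjusted mean: 0.64/[(2/13) x 0.50] = 8.32; 0.64/[(2/13) x 0.36] = 11.56.

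| Power, 2 x 3, n = 13 | r = 0.5 | r = 0.7 | r = 0.85 |
|---|---|---|---|
| *Constant effect:* main effect | 0.36 | 0.31 | 0.28 |
| group x time | 0.52 | 0.75 | 0.97 |
| adjusted post-baseline mean | 0.77 | 0.89 | 0.99 |
| *Effect at acquisition only:* main effect | 0.13 | 0.11 | 0.11 |
| group x time | 0.52 | 0.75 | 0.97 |
| adjusted post-baseline mean | 0.27 | 0.36 | 0.57 |
| adjusted difference at acquisition | 0.60 | 0.76 | 0.95 |

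Simulation of the constant-effect case at r = 0.5 and 0.7 agrees within about 0.02.

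**Source of the gap to group x time.** A 1-df contrast on mean change from baseline (variance (2/n)[(1+r)/2 + 1 - 2r]) has power 0.62 / 0.83 at r = 0.5 / 0.7. At r = 0.7 the step from 0.75 to 0.83 comes from using 1 df instead of 2, and the step from 0.83 to 0.89 comes from covariate adjustment.

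**Other layouts, constant effect** (main / group x time / adjusted mean):
- 2 x 4, n = 13, r = 0.5: 0.46 / 0.51 / 0.84. This assumes nobody is lost before long-term retention.
- Phase I, 2 x 4, n = 6, r = 0.5: 0.22 / 0.24 / 0.45. At r = 0.7: 0.19 / 0.38 / 0.56.

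**The case against.** The strongest reply is that the plan never says it reads the group main effect. Its wording about the different timepoints leans towards group x time, where baseline is the reference and nothing is averaged away. That stands. A reader might infer that the trial's test is diluted by construction, but the documents support this only if the main effect is the term used.

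A reader might also infer that group x time throws away the correlation with baseline. It does not: its error variance is proportional to 1-r, and its power rises from 0.52 to 0.75 to 0.97 as r goes from 0.5 to 0.7 to 0.85. Its shortfall comes from the omnibus degrees of freedom and from using unadjusted change.

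The constant-effect scenario also favours adjustment of the overall mean. Focus instructions differ only at acquisition, and Procedures reports that motor learning was not significant on Phase I retention data, so an effect mainly at acquisition is at least as plausible. In that case an overall adjusted average is itself diluted and does worse than the existing interaction (0.27 / 0.36 against 0.52 / 0.75 at r = 0.5 / 0.7). This stands, and it shapes the fix.

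Finally, the text is retrospective and the study is one of feasibility, so changing the model now is a reanalysis. This limits what can be claimed for the completed phases. It does not remove the need to name the test, or the value of the change for the next study.

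**Conclusion.** The point holds in this form: baseline is a time level, it is not adjusted for, and the term that tests focus of attention is not named. The shrinkage to 2/3 or 3/4 is exact for a constant effect, but applies only to the group main effect. Against group x time, the gain from adjustment depends on quantities the documents do not give. With 13 per arm, the 2 x 3 layout and a constant 0.8 SD effect, it is 0.25 in power at r = 0.5 and 0.14 at r = 0.7. It is about 0.02 at r = 0.85. For an acquisition-only effect, the adjusted acquisition contrast gains 0.08 at r = 0.5 and essentially nothing from r = 0.7 upwards.

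The argument is firmest for Phase II, where concealment until after baseline is described. In Phase I, allocation alternated after the first man and first woman, so equal expected baselines are less secure, although the focus instructions still came only at acquisition.

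A reader might infer that Phase I missed a real effect. The documents do not show that. With 6 per arm, adjustment would have given only about 0.45 power at r = 0.5 under the same assumptions, so the Phase I result would have been inconclusive with either model.

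**What to change.** In both phases, take baseline out of the time factor. Use acquisition, short-term retention and, where analysed, long-term retention as the levels, with terms for group, time, group x time, baseline excursion and baseline x time.

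Name the baseline-adjusted group difference at acquisition and at each retention timepoint as the tests of focus of attention, each with a 95% CI, and state one of them as primary. Do not rely on the average over timepoints alone, because it dilutes an effect confined to acquisition. Treat the Phase II shoulder angle in the same way, with its own baseline value. Raw changes from baseline can be shown as description.

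The cost is a few residual degrees of freedom and no new data, since baseline is already one of the collection points. If the model is applied to the completed phases, label the result a reanalysis made after the findings were known. Carry the model into the protocol of the planned randomized study.

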## **Investigators**

Although the principal investigators were both faculty members at Western Carolina University, one of which was a licensed physical therapist, the other investigators were student physical therapists. During Phase I, each investigator filled one of three roles during data collection for the entire phase: script reading, computer management, or patient guarding. Lack of cross-training created difficulty in data collection, therefore in Phase II investigators were trained for all roles. Different student groups conducted each phase of the feasibility study and were trained primarily by the previous student group. Inconsistencies with both instruction and data collection persisted suggesting changes in investigator training are necessary prior to a randomized controlled study.

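### Timepoint differences are planned only after a significant overall model, which distorts them on average at 12 and 26 participants; report every difference with an interval

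*Combined protocol and SAP*

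**What the plan says.** The Study design section describes a "two phase feasibility study". Recruitment and retention gives the sizes: "Twelve adults with chronic stroke" in Phase I and "Twenty-six adults post-acute stroke" in Phase II.

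In Data analyses, Phase I has a model with two groups and four timepoints ("For Phase I, a 2 (group) X 4 (time) repeated measures mixed model ANOVA was" is how the sentence begins). For the second phase, "Phase II utilized both a 2 (group) X 3 (time) and 2 (group) X 4 (time) mixed model ANOVA"; the four-timepoint analysis is kept separate because of high attrition, for which no figure is given.

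The rule at issue is: "When the overall model was significant, the post hoc pairwise comparison was used, with a Bonferroni correction". Its stated purpose is "to examine differences between every two timepoints in each group", so the conditional comparisons are within-group. The rule does not say whether the time effect, the group effect or the interaction must be significant, and no significance level is given.

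The only other outcome result that the section promises is F values, with corrected degrees of freedom if sphericity fails. Means and SDs are introduced as a summary of participant characteristics. No outcome difference, confidence interval, SD by timepoint or correlation between timepoints is promised independently of significance.

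A later randomised study appears in the Investigators section, which says that "changes in investigator training are necessary prior to a randomized controlled study".

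**The concern.** A test with low power is passed more often when sampling error has enlarged the differences it responds to. Estimates examined only after passing it are therefore a selected set, and their average is not the true value. When the test is not passed, the plan names no estimate at all, and a bare non-significant F from about six people per arm says little about what could be excluded.

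Significance already steered the design. The Setting section cites the non-significant Phase I group result, with findings of other studies, in moving Phase II to acute stroke. Procedures ties the increase to six acquisition trials to non-significant Phase I retention data. An interval would have shown how large an effect Phase I left open.

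If a later randomised study drew on these results, it would need a difference, an SD and a correlation. The plan as written promises none of them free of selection.

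**Working it through.** **No figure to reproduce.** Data analyses mentions a power analysis but gives no effect size, SD, power or target number. The effect of the gate was therefore simulated.

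**Inputs from the documents.** 12 and 26 participants; two groups; three or four timepoints. Pairs of timepoints per group are k(k−1)/2, which is 3 for k = 3 and 6 for k = 4.

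**Assumptions.** Equal arms (12/2 = 6 and 26/2 = 13), two-sided level 0.05, normal data with SD 1, sphericity, correlation ρ of 0.5 to 0.7. Attrition would make the four-timepoint Phase II analysis smaller than 13 per arm.

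**Why selection matters at these sizes.** The standard error of a within-group change is √(2(1−ρ)/n).
- n = 13, ρ = 0.7: √(0.6/13) = 0.21 SD.
- n = 6, ρ = 0.5: √(1/6) = 0.41 SD.

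A true change of 0.2 SD is thus between about half a standard error and one standard error.

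**Gate on the time effect.** The test is F = MS(time)/MS(error) on k−1 and 2(n−1)(k−1) degrees of freedom. The table gives the mean within-group change among runs passing the gate, divided by the true change, with the share of runs passing in brackets. Here ρ = 0.7 and both arms change by the same amount at acquisition only; 40,000 runs per setting.

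| Per arm, model | 0.2 SD | 0.5 SD | 0.8 SD | 1.2 SD |
|---|---|---|---|---|
| 6, 2×4 | 2.06 (12%) | 1.23 (56%) | 1.02 (95%) | 1.00 (100%) |
| 13, 2×3 | 1.74 (24%) | 1.04 (92%) | 1.00 (100%) | 1.00 (100%) |
| 13, 2×4 | 1.67 (23%) | 1.04 (92%) | 1.00 (100%) | 1.00 (100%) |

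At a true 0.2 SD, varying ρ from 0.5 to 0.7 and letting the other arm change by the same amount or by 0.3 to 0.4 SD more widens the range to about 1.2 to 2.4. The high end is 6 per arm, ρ = 0.5 and equal changes. The low end is 13 per arm, ρ = 0.7 and the other arm changing by 0.4 SD more; in the 2×3 model, for example, the mean is about 0.25 SD and 0.25/0.2 = 1.25.

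**Gate on the interaction, within-group change.** With 13 per arm, 2×3, and arms truly changing by 0.2 SD and by 0.3 to 0.4 SD more than that, the lesser-changing arm's 0.2 SD averages about −0.05 to 0.05 SD among runs passing. The distortion is towards zero.

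**Between-arm difference in change, if it too were reported only when the interaction is significant.** With 13 per arm, 2×3 and ρ of 0.5 to 0.7, a true 0.3 SD passes in 11 to 15% of runs. It then averages 0.63 to 0.76 SD, against 0.30 SD over all runs: 0.63/0.3 = 2.1 and 0.76/0.3 = 2.5. With one arm changing at acquisition only and ρ = 0.7, the ratios are:

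| Per arm, model | 0.2 SD | 0.5 SD | 0.8 SD | 1.2 SD |
|---|---|---|---|---|
| 6, 2×4 | 2.64 (7%) | 1.82 (16%) | 1.39 (38%) | 1.12 (74%) |
| 13, 2×3 | 2.66 (10%) | 1.49 (36%) | 1.13 (75%) | 1.01 (98%) |
| 13, 2×4 | 2.42 (9%) | 1.45 (35%) | 1.12 (76%) | 1.01 (99%) |

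**Without the gate** the mean estimate equals the truth in these settings (0.50 for a true 0.5 SD).

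**The case against.** The case for leaving the rule alone has four parts.

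- **No carry-over is planned.** A reader might infer that the randomised study will be sized from these estimates, and that a doubled effect would give it (1/2)² = a quarter of the sample it needs. The documents do not support this. The stated aims are feasibility aims, the later study is mentioned only in connection with investigator training, and the power analysis is linked only to recruitment and retention goals. This stands: harm to a later trial is conditional.
- **The gated comparisons are within-group.** The doubling arises for the between-arm difference in change, which the ANOVA tests directly and which is not among the post hoc comparisons. This stands, and it is a second reason why the quarter-sample inference fails.
- **Nothing says outcome data are withheld.** The sentence governs the use of a post hoc comparison, and the Phase I null result is disclosed. This stands, but silence on outcome tables is not a plan to report estimates with intervals.
- **The inflation may be small.** Under a time gate with 13 per arm it is 1.04 times at 0.5 SD (ρ = 0.7). A larger figure is available: a true 0.2 SD change that is also significant after Bonferroni averages 0.56 to 0.72 SD. It applies only if non-significant pairs go unreported, which the plan does not say. This stands as a limit on size. It does not help where the true change is small or the arms have six people.

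A reader might also infer that every gated estimate is too large. That is false: the bias is an average, and under an interaction gate it can run towards zero.

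**Conclusion.** The concern holds in a limited form. The plan makes within-group timepoint differences conditional on an overall test, leaves the triggering term unstated, and promises no unconditional outcome estimates. At these sample sizes the condition distorts what it lets through when power at the gate is low, and has almost no effect when power is high. Its size cannot be fixed from the documents, because the triggering term, the true effects and the correlations are not given; every simulation input other than the two sample sizes and the numbers of groups and timepoints is an assumption. What is established is a reporting weakness. It is not established that a later trial would be undersized.

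**What to change.** Delete the condition that the overall model be significant. In both phases, and for each model fitted, report the following whatever the F test shows:

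- every planned timepoint difference in each group, with a confidence interval;
- the between-group difference in change, with a confidence interval;
- the SD at each timepoint and the correlations between timepoints.

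Keep the Bonferroni correction for claims of significance. It already deals with the multiplicity of the pairwise tests, so the gate is not needed for that. Add a sentence that, if a later trial uses these figures, they will not be selected by significance. This does not commit anyone to using them.

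The cost is a change of wording and one extra table from data already in the analysis. The drawback is that most intervals will be wide and will include zero.
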